### 6.2 Waiver or Alteration of Authorization for the Uses and Disclosures of PHI

#### 6.2.1 Access, use or disclosure of PHI representing no more than a minimal risk to the privacy of the individual

##### 6.2.1.1 Plan to protect PHI from improper use or disclosure

Include the following statement as written – DO NOT ALTER OR DELETE unless this section is not applicable because the research does not involve a waiver of authorization. **If the section is not applicable, remove the statement and indicate as not applicable.**

Not applicable.

**6.2.1.2 Plan to destroy identifiers or a justification for retaining identifiers**

Describe the plan to destroy the identifiers at the earliest opportunity consistent with the conduct of the research. Include when and how identifiers will be destroyed. If identifiers will be retained, provide the legal, health or research justification for retaining the identifiers.

NA

**6.2.2 Explanation for why the research could not practicably be conducted without access to and use of PHI**

Provide an explanation for why the research could not practicably be conducted without access to and use of PHI.

NA

**6.2.3 Explanation for why the research could not practicably be conducted without the waiver or alteration of authorization**

Provide an explanation for why the research could not practicably be conducted without the waiver or alteration of authorization.

NA

**6.3 Waiver or alteration of authorization statements of agreement**

By submitting this study for review with a waiver of authorization, you agree to the following statement – DO NOT ALTER OR DELETE unless this section is not applicable because the research does not involve a waiver or alteration of authorization. **If the section is not applicable, remove the statement and indicate as not applicable.**

Not applicable.

**7.0 Study Design and Procedures**

Data collection materials that will be seen or used by subjects in your study must be uploaded to CATS IRB (<http://irb.psu.edu>). **DO NOT** include any actual data collection materials in this protocol (e.g., actual survey or interview questions)

[Do not type here]

**7.1 Study Design**

Describe and explain the study design.

This study design is a cluster randomized trial. Schools will be randomized to implement either the Aevidum curriculum alone (n=5) or Aevidum curriculum plus club activities (n=5). Students in grades 9-12 at each school whose parents did not opt them out will be asked to complete pre- and post-surveys. School staff who participated in the Aevidum curriculum training will be asked to complete the “Educator Training Feedback Survey”.

## 7.2 Study Procedures

Provide a step by step description of all research procedures being conducted (broken down by visit, if applicable) including such information as below (where and when applicable); describe the following:

- HOW: (e.g., data collection via interviews, focus groups, forms such as surveys and questionnaires, medical/school records, audio/video/digital recordings, photographs, EKG procedures, MRI, mobile devices such as electronic tablets/cell phones, observations, collection of specimens, experimental drug/device testing, manipulation of behavior/use of deception, computer games, etc.)
- WHERE: (e.g., classrooms, labs, internet/online, places of business, medical settings, public spaces, etc.)

Partnering with 10 high schools to evaluate the effectiveness of the Aevidum curriculum (plus/minus club) to improve adolescent mental health knowledge, help-seeking intentions, and school culture. Prior to the start of the 2021-2022 academic year, schools will be recruited and randomly assigned to implement the Aevidum curriculum (n=5) or the curriculum and club (n=5). Regardless of the research, the schools have the autonomy to introduce the intervention(s) (Aevidum curriculum plus/minus club) on their own. The Aevidum curriculum will be delivered to only 9th grade students in their health classes.

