### 3.1 Inclusion Criteria

Create a numbered list of the inclusion criteria that define who will be included in your final study sample (e.g., age, gender, condition, etc.)

1. Students (grades 9-12) and staff from participating schools. For the first time during the 2021-2022 school year, all participating schools will be implementing the Aevidum curriculum, but only half of the participating schools will implement club activities in addition to the curriculum (n=5 schools will implement just the curriculum, and n=5 schools will implement the curriculum AND club activities).

School staff who participated in the Aevidum Training will be asked to complete a brief survey using our “Educator Training Feedback Survey” (included in supporting documents).

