### 3.3 Early Withdrawal of Subjects

#### 3.3.1 Criteria for removal from study

Insert subject withdrawal criteria (e.g., safety reasons, failure of subject to adhere to protocol requirements, subject consent withdrawal, disease progression, etc.).

The intervention (Aevidum curriculum plus/minus club) will happen regardless of the research. These materials are already freely available and being utilized in schools across the Commonwealth. The research pieces are the student pre-post questionnaires and staff interviews to assess knowledge change, help-seeking and school culture/climate. student participants whose parents did not opt-them out may voluntarily withdraw from the study at any time by declining to have their child complete the pre and post survey.

School staff that participate in interviews at the end of the school year may also decline to answer any demographic questions or interview questions that they do not feel comfortable answering.

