#### **4.2.1 How potential subjects will be recruited.**

Schools will be recruited via email communication (See attached School Recruitment Email and Aevidum One Pager) in partnership with the Executive Director of Aevidum, [name]. We anticipate beginning recruitment efforts by reaching out to schools who have already expressed interest in Aevidum and/or schools that PRO Wellness and Aevidum already have a connection with. Schools currently utilize the Aevidum curriculum and run club activities independent of the proposed research work (student pre-post surveys and staff interviews). Educators who completed the Aevidum Training will be contacted to complete the “Educator Training Feedback Survey”.

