### Schools

The 5 of the 10 schools that are randomly assigned to implement 2 Aevidum club activities will receive a \$1,000 stipend to support club activities during the 21-22 academic school year. The remaining 5 schools who are randomly assigned to implement just the Aevidum curriculum will receive a \$1,000 stipend for club activities at the end of the 2021-2022 school year after completion of the research.

An incentive will be offered to schools who have post-survey completion rates of 60%. Schools who hit this goal will be sent an additional \$100 stipend to put towards their Aevidum club.

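### Curriculum-only schools could start an Aevidum club during the study year; nothing asks them to wait or records it, which leaves the secondary club contrast and the Aim 1 attribution unprotected

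*Combined protocol and SAP*

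**What the plan says.** The allocation is clear in Section 7.1: "Schools will be randomized to implement either the Aevidum curriculum alone (n=5) or Aevidum curriculum plus club activities (n=5"). Section 3.1 adds: "For the first time during the 2021-2022 school year, all participating schools will be implementing the Aevidum curriculum", and says that club activities will run in half of the schools. Section 1.1 describes the club arm as starting a club.

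Section 7.2, immediately after describing the assignment, says: "Regardless of the research, the schools have the autonomy to introduce the intervention(s) (Aevidum curriculum plus/minus club) on their own". Section 3.3.1 says of the intervention: "These materials are already freely available and being utilized in schools across the Commonwealth". Section 1.1 places the club processes and event ideas on the Aevidum website. Under Section 4.2.1, recruitment begins by "reaching out to schools who have already expressed interest in Aevidum and/or schools that PRO Wellness and Aevidum already have a connection with".

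On money, Section 13.0 says: "The remaining 5 schools who are randomly assigned to implement just the Aevidum curriculum will receive a" $1,000 club stipend, payable only when the school year and the research are over. It also offers $100 towards a school's Aevidum club for reaching 60% post-survey completion, without limiting this to the club arm.

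The exclusions in Section 3.2 apply to students and staff. None applies to schools. Section 8.3 makes the within-arm change over time the primary analysis, each arm separately, and the direct comparison of arms (group by time) a secondary one.

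**The concern.** The group-by-time interaction is the only randomised estimate of what the club adds. It depends on the curriculum-only schools not running a club between the pre-survey (September-October 2021) and the post-survey (April-May 2022). The protocol states that intention but has no provision that secures it. There is no deferral request, no record of club activity in the comparator arm, and no stated handling of a school that adds a club. The schools approached first are those with an interest in Aevidum or a link to it or to the study team, and some of them may well want a club.

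Two estimates are exposed. The club contrast would be biased toward zero if clubs have an effect. The primary Aim 1 estimate, a pre-post change credited to the curriculum, would absorb part of any club effect on knowledge and help-seeking. With no untreated arm, the two could not be separated afterwards.

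**Working it through.** **Inputs from the protocol.** Five schools per arm (Sections 3.1, 4.1, 7.1, 7.2); Section 1.1 also gives six per arm alongside a total of 10 schools, which needs reconciling. Nearly 1,000 students in 10 schools (Section 8.1), so about 100 per school. Results are reported with 95% confidence intervals (Section 8.3), taken here as two-sided 0.05. Section 8.2 rests the sample size on feasibility and gives no power, effect size, standard deviation, intraclass correlation or contamination allowance, so there is no plan figure to reproduce.

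**Dilution of the club contrast.** Let D be the true club effect on change, c the number of comparator schools that start a club after the pre-survey, and f the fraction of D such a club delivers. With equal school weights:

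expected contrast = D × (1 − f × c/5)

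- f = 1, c = 1: 1 − 1/5 = 0.80, a loss of 20%
- f = 1, c = 2: 1 − 2/5 = 0.60, a loss of 40%
- f = 0.5 (assumed), c = 1: 1 − 0.5/5 = 0.90, a loss of 10%

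With six schools per arm, the most one school could remove would be 1/6, or about 17%.

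**Aim 1.** The expected pre-post change in the curriculum-only arm becomes the change without clubs plus f × (c/5) × (club effect on that outcome). One full-effect club adds 20% of the club effect on knowledge or help-seeking. If clubs do not affect those outcomes, it adds nothing.

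**Illustration of the cost in power (assumptions, not plan figures).** Take a t-test on school-level changes, 5 against 5, with 8 degrees of freedom. An effect of 2.02 school-level standard deviations has 80% power without contamination (noncentrality 2.02/√(2/5) = 3.2). With f = 1:

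| Comparator schools with a club | Contrast left | Power, mean dilution only | Power, simulated | Schools needed, 1/(1 − c/5)² |
|---|---|---|---|---|
| 0 | 100% | 80% | 80% | 1.00 times |
| 1 | 80% | 61% | 47% | 1.56 times |
| 2 | 60% | 39% | 22% | 2.78 times |

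The simulated column (200,000 runs per row) is lower because a mixture of schools with and without a club also widens the spread within the comparator arm.

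In standard deviations of individual change, with 100 students per school and an assumed intraclass correlation of change of 0.01 to 0.05, the effect detectable at 80% power is 0.29 to 0.49. Counting mean dilution only, the true effect would have to be 0.36 to 0.62 with one such school (divide by 0.8) and 0.48 to 0.82 with two (divide by 0.6).

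**A club that predates the pre-survey.** The contrast is in change over time. An established club's effect in a comparator school is at least partly in the baseline response, so the 20% figure does not carry over to that case.

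**The case against.** The autonomy sentence can be read as ethics-board language: the programme exists outside the research, and schools could adopt it without the study. Sections 3.3.1, 4.2.1 and 5.6.3.1 make the same point. On that reading it does not license an enrolled school to disregard its assignment. Section 7.1 assigns schools to the curriculum alone, and Section 3.1 limits clubs to half of them, so a comparator school that starts a club departs from its allocation. It would be wrong to infer that it breaks no rule. This stands in part. The allocation is stated, but nothing protects it, and the sentence as written covers the club.

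A reader might also infer that some curriculum-only schools already have clubs, because Section 4.2.1 says: "Schools currently utilize the Aevidum curriculum and run club activities independent of the proposed research work (student pre-post surveys and staff interviews"). The documents do not support that. The sentence may describe schools in general, a connection may be only with the study team, and Section 1.1 has club-arm schools starting a club. An existing club is not excluded either, since first-time use in Section 3.1 is tied to the curriculum.

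Three further points stand. The deferred stipend lowers the incentive to start early, and Section 1.1 describes the kickoff training only for the club arm, so a self-started club may fall short of the full effect. The contrast affected is secondary. And the recruitment email, one-pager and signed school form are not available here; deferral terms could be in them.

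**Conclusion.** The gap is real but limited. A curriculum-only school could start a club during the year, and the protocol would neither discourage this in terms nor detect it. The loss is at most 20% of the true club effect per affected school out of five. That bound assumes equal school weights, a club started after the pre-survey, and a full club effect in that school; a later or weaker club costs less. The Aim 1 estimate is affected only as far as clubs change knowledge or help-seeking.

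It would go too far to say that the contrast is diluted. No contamination is documented and no rate is given, so the supported statement is that it could be. Nor would a stray club empty the curriculum-only arm of meaning: Aim 1 concerns knowledge and help-seeking, while the benefits the club is expected to add are mainly in environment, stigma and visibility. The case for change rests on how little the protection costs and on this being the only randomised evidence about the club.

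**What to change.** 1. In Sections 3.1/3.2, add a school-level criterion: no Aevidum club at the school at randomisation. This makes explicit what Section 1.1 assumes. Apply it to any replacement school from the waitlist as well.
2. In Section 7.2, and with the school approval already obtained under Section 16.1, have each school agree before randomisation that, if assigned to curriculum only, it will defer a club until its post-survey closes. Reword the autonomy sentence to fit: schools are free to decline the study, and those that join agree to this timing.
3. Record club activity in all 10 schools at baseline and at the end of the year. In Section 8.3, state that schools are analysed as assigned, and add a sensitivity analysis by actual club exposure.

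Making the end-of-year stipend conditional on waiting is optional; the remedy does not depend on it.

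The cost is a few sentences, one addition to the school approval and a short activity record. Some interested schools would become ineligible or would have to wait. The documents do not say how many, but the waitlist in Section 8.2 and the end-of-year stipend in Section 13.0 already make room for this.

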### Student Pre- and Post- Survey

To measure aims 1 and 2, pre- and post-surveys (see attached, using the University of Michigan Depression Center (UMDC) Peer-to-Peer Depression Awareness Assessment) will be completed by students in grades 9th – 12th at all 10 participating schools. All eligible students whose parents did not opt them out from pre-post survey completion will be provided a link to participate in the REDCap survey. This link will be provided directly by the school. Subjects will be provided a link to review the study information and provide their email address if they wish to participate in the post-survey. The consent process will take place prior to completing the demographic and survey, as participants will be provided the Summary Explanation of Research and be notified that their completion of the demographic questionnaire implies their voluntary consent to participate in the research.

### School Staff Semi-structured Interviews

Zoom interviews (maximum of 50) will be conducted with two school staff members from each school to measure Aevidum's impact on school mental health referrals and school climate indicators. School staff members will be identified by the school contact and invited to participate. Participants will be instructed to turn off their camera and the interview will be recorded (only voices) via PSH HIPAA Compliant Zoom. Interviews will begin with introductions and information on the project. Participants will have the opportunity to ask questions about the study. See School Staff Demographics and Interview Guide to view open-ended questions to address study aims.

### Analysis of Zoom Interview Data:

Rev.com, a professional service will be used by the research team to transcribe the audio recordings. Transcripts will be uploaded into a qualitative software system (Nvivo 12 plus). 20% of the transcripts will be coded independently using a codebook developed by the research team by two team members until an acceptable inter-rater reliability score is achieved. Once the coding process is complete, the team will meet to identify themes.

Additionally, we will recruit school staff members who participated in the Aevidum curriculum training to complete the "Educator Training Feedback Survey". We are not collecting any PHI, nor will names of the school staff participants be disclosed in the use of manuscripts/ written publications.

### **7.2.1 Visit 1 or Day 1 or Pre-test, etc.**

Provide a description of what procedures will be performed on visit 1 or day 1 or pre-test in order of how these will be done. If your study only involves one session or visit, use this section only and indicate 7.2.2 as not applicable.

#### **Student Pre- and Post- Survey**

The pre-survey will be completed by students in grades 9th – 12th at all 10 participating schools at the beginning of the school year (September-October 2021). All eligible students will be provided a link to participate in the REDCap survey. This link will be provided directly by the school. Subjects will be provided a link to review the study information and provide their email address if they wish to participate in the post-survey. The consent process will take place prior to completing the demographic and survey, as participants will be provided the Summary Explanation of Research and be notified that their completion of the demographic questionnaire implies their voluntary consent to participate in the research. Demographics will include sex, age (in years), race/ethnicity and grade. Once students complete the post-survey, their email addresses will be unlinked from their survey responses.

#### **School Staff Semi-structured Interviews**

Semi-structured interviews will also be conducted with up to 5 school staff members at the end of the school year. The main point of contact at the school will identify interested subjects who will be provided a link to review the Summary Explanation of Research, determine eligibility and indicate assent by completion of the demographic survey. Eligible school staff will be contacted by the study team to schedule their interview based on their availability. Up to two participants may be interviewed at the same time. Prior to the Zoom interviews participants will be reminded that their completion in the interview implies their voluntary consent to participate in the research.

### **7.2.2 Visit 2 or Day 2 or Post-test, etc. (If applicable)**

Provide a description of what procedures will be performed on visit 2 or day 2 or post-test in order of how these will be done. If your study involves more than two sessions or visits replicate this section for each additional session or visit (e.g., 7.2.3, 7.2.4, etc.).

At the end of the school year (April-May 2022), students who participated in the pre-survey will receive the post-survey via REDCap invitation to the email provided during the pre-survey.

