#### **4.2.4 Describe the eligibility screening process and indicate whether the screening process will occur before or after obtaining informed consent. Screening begins when the investigator obtains information about or from a prospective participant in order to determine their eligibility. In some studies, these procedures may not take place unless HIPAA Authorization is obtained OR a waiver of HIPAA Authorization when applicable for the screening procedures is approved by the IRB. [For FDA regulated studies, consent for any screening activities would need to be obtained prior to screening unless specifically waived by the IRB.]**

Schools will provide the REDCap link to all eligible students during the school day to complete the pre-survey. Students will be asked to provide their email address at this time so they can complete the post-survey following curriculum completion. Once students complete the post-survey, email addresses will be unlinked from survey responses.

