#### **Student Pre- and Post- Survey**

All eligible students will be provided a link to participate in the REDCap survey. This link will be provided directly by the school using a method that works best for them. The study team will suggest that schools either 1) Send an email to the student’s school email addresses with the link (see attached “Student Pre Survey Email Invitation”) or 2) Instruct their teachers to write the link on their whiteboards for students to enter directly into their school computer’s web browser. Subjects who follow the link will review the study information and provide their email address if they wish to participate in the post-survey. The consent process will take place prior to completing the demographics and survey, as participants will be provided the Summary Explanation of Research and be notified that their completion of the demographic questionnaire implies their voluntary consent to participate in the research.

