### Student Pre- and Post- Survey

In primary statistical analysis, schools implementing only the curriculum (Aim 1) and schools implementing the curriculum and club activities (Aim 2) will be analyzed separately, using the same methods. Descriptive statistics will be calculated and survey items will be presented graphically over time. Mixed effects linear and logistic regression models appropriate for longitudinal (repeated measures) data will be used to analyze all survey items collected at each time point. The models will contain a fixed effect for time (pre vs. post) and random effects for school and student. The parameter for time is the primary parameter of interest in the model, as it indicates the change over time with intervention implementation. Parameter estimates and standard errors from the models will be reported along with corresponding 95% confidence intervals and p-values.

In secondary statistical analysis, we will compare the curriculum-only schools to the curriculum plus club activities schools directly.

Specifically: 1) Compare students from schools in Aim 1 (curriculum only) to those in Aim 2 (curriculum plus club) regarding changes in knowledge, help-seeking behavior, school environment/stigma and program visibility.

2) Compare the impact on 9th graders in curriculum schools versus 9th graders in curriculum plus club schools.

The same mixed effects regression models will be used for each survey item, except that the model will also include fixed effects for group (curriculum-only vs. curriculum plus club activities) and a group by time interaction effect. A positive interaction effect indicates that schools which implemented curriculum and club activities had larger changes over time than curriculum alone.

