## 15.0 Resources Available

### 15.1 Facilities and locations

Identify and describe the facilities, sites and locations where recruitment and study procedures will be performed.

If research will be conducted outside the United States, describe site-specific regulations or customs affecting the research, and describe the process for obtaining local ethical review. Also, describe the principal investigator's experience conducting research at these locations and familiarity with local culture.

Pre- and post- surveys will be completed during the school day. Zoom interviews with school staff will take place at a pre-determined time with the interviewer and study participant and will occur using the PSH HIPAA Compliant Zoom platforms (audio recorded only, no video).

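### The post-survey is sent only by email to an address students may leave, so all post data behind the primary time effect pass two voluntary steps, and section 8.3 does not address non-response.

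*Combined protocol and SAP*

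**What the plan says.** **Baseline.** Section 4.2.4: "Schools will provide the REDCap link to all eligible students during the school day to complete the pre-survey". Section 5.2.1 leaves the method to the school and suggests two: an email to students' "school email addresses with the link", or "Instruct their teachers to write the link on their whiteboards for students to enter directly into their school computer".

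**The address.** Sections 5.2.1, 7.2 and 7.2.1 have students "provide their email address if they wish to participate in the post-survey". Section 4.2.1 instead treats the address as something every student gives, because it links the two surveys. Section 4.2.4 says students will be asked for it.

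**Follow-up.** Section 7.2.2, for April-May 2022: "students who participated in the pre-survey will receive the post-survey via REDCap invitation to the email provided during the pre-survey". Section 4.2.1 gives the same route. No section describes a post-survey link handed out by the school. Section 15.1 nevertheless says "Pre- and post- surveys will be completed during the school day".

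**Retention.** The gift-card drawing rises from $20 after the pre-survey to $30 after the post-survey, with four winners per school each time (section 13.0). Also in section 13.0: "An incentive will be offered to schools who have post-survey completion rates of 60" per cent, the incentive being $100 per school.

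**Analysis.** Section 8.3: "The models will contain a fixed effect for time (pre vs. post) and random effects for school and student". The time parameter is primary and is estimated separately in each arm. The section states no handling of missing post-surveys, no comparison of responders with non-responders and no sensitivity analysis.

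**The concern.** Baseline reaches every eligible student through the school. Follow-up reaches a student only if an address was left in September-October 2021 and an email is answered six to eight months later. A student who leaves no address has no written route to a post-survey, yet 7.2.2 assumes that every pre-survey participant receives one.

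If students who pass both steps changed by a different amount from those who do not, the estimated time effect is not the change in the surveyed students. With no untreated arm in the primary analysis, nothing else in the estimate would reveal this. Post-surveys not collected in spring 2022 cannot be recovered later, so the delivery route matters more than any later adjustment.

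**Working it through.** The plan gives no expected completion rate and no power calculation (section 8.2 rests on feasibility), so there is no figure of its own to reproduce. The numbers below are illustrations.

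**1. Students involved.** Section 8.1 gives nearly 1,000 students. If all complete the pre-survey and 60% the post-survey (both assumed), 0.60 × 1,000 = 600 give post data and about 400 do not.

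**2. Responders against everyone.** Let r be the response rate and d the responders' mean change minus the non-responders', in SD units.

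- Overall change = r × (responders' change) + (1 − r) × (non-responders' change).
- Hence responders' change − overall change = (1 − r) × d.

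| r (assumed) | d = 0.1 | d = 0.25 | d = 0.5 |
|---|---|---|---|
| 0.60 | 0.04 | 0.10 | 0.20 |
| 0.40 | 0.06 | 0.15 | 0.30 |

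A negative d reverses the sign. This formula describes the raw change in responders, not the planned estimator.

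**3. The planned type of model.** I simulated 1,000,000 students with true change 0, pre-post correlation 0.5, logistic response with slope 0.5 per SD and no clustering (all assumed). The random-intercept likelihood estimate keeps pre-only students. Treating the variance components as known or estimating them gives the same two-decimal results.

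| Response depends on | Raw change in responders, 60% / 40% response | Mixed model, 60% / 40% response |
|---|---|---|
| pre-score only | −0.09 / −0.14 | 0.00 / 0.00 |
| post-score | +0.09 / +0.14 | +0.14 / +0.21 |
| change itself | +0.19 / +0.28 | +0.14 / +0.21 |

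The model removes selection explained by the pre-score and leaves selection tied to the post-score or the change. The positive signs follow from the assumed positive slope.

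**4. Would baseline covariates repair this?** Grade is the natural candidate, since section 7.2 gives the curriculum to 9th graders only. Assume 9th graders are 25% of students and change by 0.4 SD, others by 0, with response 80% and 53% (60% overall) and correlation 0.5. The true mean change is 0.25 × 0.4 = 0.10.

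| Model | Equal pre-scores | 9th graders start 0.5 SD lower |
|---|---|---|
| time only (as planned) | 0.13 | 0.11 |
| plus grade main effect | 0.13 | 0.13 |
| grade-by-time, standardised to baseline grade mix | 0.10 | 0.10 |

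A main effect adjusts levels, not change. It barely helps in the first case and does harm in the second.

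**The case against.** Much can be said for the plan, and several stronger readings that a reader might infer are not supported.

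- **Classroom baseline against emailed follow-up.** The documents say school day, not class, and one of the two suggested baseline routes is itself an email. The difference that stands is who is reached: all eligible students at baseline, only those who left an address at follow-up.
- **Section 7.2.2 contradicts 15.1.** One says how the link arrives, the other when the survey is completed, and a student can open an emailed link at school. This is a tension to be reconciled. The clearer inconsistency is whether the address is optional (5.2.1, 7.2, 7.2.1) or given by all (4.2.1).
- **The plan accepts 40% loss.** Sixty per cent is a threshold for a school bonus, with no stated denominator. It is not an expected rate, and the gift-card drawings also work towards retention.
- **The improvement will be inflated.** The documents do not show this. Engaged students may start higher and have less room to improve, and the first simulated case biases the raw change downward.
- **The estimate uses volunteers alone.** A likelihood-based mixed model can keep pre-only students, although section 8.3 does not say that it will.
- **The club raises response in one arm.** This is plausible, since only one arm is assigned a club during follow-up, but it is conjecture and concerns the secondary comparison.

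What remains is that all post data pass two voluntary steps and section 8.3 has no answer to response related to the outcome.

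**Conclusion.** The point holds as a gap in follow-up delivery and in the handling of non-response, and it bears on the primary parameter. Neither the direction nor the size of the bias can be derived from the documents.

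Under an assumed 60% completion, the change in responders departs from the overall change by 0.04 to 0.20 SD for d from 0.1 to 0.5 SD. The planned model can do better or worse than that raw figure: unbiased if response depends only on the pre-score, about 0.14 SD off at 60% response in the two outcome-dependent cases simulated. Those results rest on the assumed correlation, response slope and absence of clustering, and the SD scale suits the items analysed by linear rather than logistic models.

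The case for change does not need a proven bias. The remedy is cheap and brings 7.2.2 into line with what 15.1 already states.

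**What to change.** **Section 7.2.2.** Have each school give the post-survey link to pre-survey participants during the school day in April-May 2022, by the route it used for the pre-survey. Use the student's email as the matching key and keep the REDCap invitation as a reminder. Participation stays voluntary.

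**Sections 4.2.1, 5.2.1, 7.2 and 7.2.1.** Reconcile whether the address is optional or expected of all. State a matching rule, applied before addresses are unlinked from responses.

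**Section 8.3.** State that students with only a pre-survey stay in the mixed model. Add one sensitivity analysis that shifts non-responders' change by a range of values, set separately by arm. A shift of δ below the modelled value lowers the estimated overall change by (1 − r) × δ. Equal shifts at equal response cancel between arms; at 60% response in both, a shift of 0.25 SD in one arm only moves the group-by-time effect by 0.4 × 0.25 = 0.10 SD. Do not rely on covariate main effects. If grade is used, include grade-by-time and standardise to the baseline grade mix.

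**Cost.** One survey sitting of 10-15 minutes (section 7.3) of school time at each school, plus revised wording. Section 15.1 promises the school day rather than class time, so schools must agree to this. Some addresses will be mistyped or unmatched, and without the matching rule one student could be counted as two.
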